## 9.5. Study Size

This is a retrospective observational study using a sample afforded by the I-Seha Electronic health record. While this study will be descriptive in nature, feasibility queries show that, between 16 February 2022 and 30 November 2022, there were 8263 patients that met all study inclusion and exclusion criteria eligible for Paxlovid™ therapy of whom at least 3000 patients were treated with Paxlovid™ therapy and 1000 were not. All records from the participant cohort of 8263 will be reviewed.

## 9.6. Data Management

EHR data will be obtained via a retrospective review of participant charts and used to discern participant-reported symptom onset, symptom duration, and relevant laboratory findings for diagnostic criteria or other related information described in [Table 2](#) and [Table 3](#).

The unstructured data that is extracted will be put into the eCRF, will then be anonymized by the clinical research assistants and presented in the format requested by the statistician at the time of analysis.

The study will abide to European GDPR legislation for maintaining confidentiality of data.

A Data Protection Impact Assessment (DPIA) will be performed to help identify and minimize the data protection risks of the study.

The EHR database is unstructured data. Individual medical records will be extracted and anonymized and populated into an eCRF. All data will be kept securely. Details of outcome measures and adverse events will be documented in hospital healthcare records. Individual research participant data is stored in an encrypted electronic database. The study investigators will adhere to hospital protocols pertaining to healthcare record use and storage to protect the research participant's identity, a unique identification code will be assigned by the Investigator, or authorized designee, to each study participant. These will be used in lieu of the participant's name, and the unique individual study code for each participant will be used for adverse events reporting and/or other study related data to be reported. This coded form of identification, instead of the participant's name, will appear on all documents/databases and will be cross-referenced by the participants date of birth (month/year). This server has managed access and password protection. The information that this server contains is backed up every 24 hours.

Personal information will be treated as confidential, but may need to be reviewed by authorized representatives of the Sponsor (such as monitors and auditors), the Contract Research Organization, the ethics committee and the regulatory authorities. The investigators and authorized designees will ensure that the confidentiality of the participants data is preserved.

### **9.6.1. Case Report Forms**

As used in this protocol, the term CRF should be understood to refer to either a paper form or an electronic data record or both, depending on the data collection method used in this study.

A CRF is required and will be completed for each included participant. The completed original CRFs are the sole property of Pfizer and should not be made available in any form to third parties, except for authorized representatives of Pfizer or appropriate regulatory authorities, without written permission from Pfizer. The party performing medical record review, Royal College of Surgeons in Ireland, Medical University of Bahrain, RCSI Bahrain, shall ensure that the CRFs are securely stored at the study site in encrypted electronic form and will be password protected to prevent access by unauthorized third parties.

RCSI Bahrain has ultimate responsibility for the collection and reporting of all clinical, safety, and laboratory data entered on the CRFs and any other data collection forms (source documents) and ensuring that they are accurate, authentic/original, attributable, complete, consistent, legible, timely (contemporaneous), enduring, and available when required. The CRFs must be signed by the investigator or by an authorized staff member to attest that the data contained on the CRFs are true. Any corrections to entries made in the CRFs or source documents must be dated, initialed, and explained (if necessary) and should not obscure the original entry.

The source documents are the hospital or the physician's chart. In these cases, data collected on the CRFs must match those charts.

### **9.6.2. Record Retention**

To enable evaluations and/or inspections/audits from regulatory authorities or Pfizer, the third party responsible for performing medical record review, RCSI Bahrain agrees to keep all study-related records, including the identity of all participating patients (sufficient information to link records, eg, eCRFs and hospital records), copies of all eCRFs, safety reporting forms, source documents, detailed records of treatment disposition, and adequate documentation of relevant correspondence (eg, letters, meeting minutes, and telephone call reports). The records should be retained by RCSI Bahrain according to local regulations or as specified in the *Statement of work*, whichever is longer. RCSI Bahrain must ensure that the records continue to be stored securely for so long as they are retained.

If RCSI Bahrain becomes unable for any reason to continue to retain study records for the required period, Pfizer should be prospectively notified. The study records must be transferred to a designee acceptable to Pfizer.

Study records must be kept for a minimum of 15 years after completion or discontinuation of the study, unless RCSI Bahrain and Pfizer have expressly agreed to a different period of retention via a separate written agreement. Record must be retained for longer than 15 years or as required by applicable local regulations.

RCSI Bahrain must obtain Pfizer's written permission before disposing of any records, even if retention requirements have been met.

## 9.7. Data Analysis

Detailed methodology for summary and statistical analyses of data collected in this study will be documented in a statistical analysis plan (SAP), which will be dated, filed, and maintained by the sponsor. The SAP may modify the plans outlined in the protocol; any major modifications of primary endpoint definitions or their analyses would be reflected in a protocol amendment.

A separate statistical analysis plan will provide analysis and programming details along with detailed table shells. A sample of the table of results expected from the primary aim of this descriptive study is listed in [Table 8](#).

All descriptive statistics will be presented as n, % for the categorical variables, or mean  $\pm$  SD, median (interquartile range) for the numerical (continuous variables), as appropriate.

Study sample will be stratified by age group: 18-29, 30-49, 50-64, 65-74,  $\geq$ 75. Numerical outcomes included the number of COVID-19 vaccines received, date of last vaccination, days from last COVID-19 vaccination to date of Paxlovid™ treatment (eg, Prescription and dispensing date), days from COVID-19 diagnosis to date of Paxlovid™ treatment (eg, dispensing date), days from COVID-19 symptom onset to date of Paxlovid™ treatment (eg, dispensing date).

Categorical outcomes included comorbid conditions and COVID-19 therapy. Possible comorbid conditions include obesity (BMI  $\geq$  30), chronic kidney disease, diabetes mellitus, primary and Secondary Immunosuppressive disease or immunosuppressive treatment, cardiovascular disease (including congenital heart disease) or hypertension, active immunosuppressive disease (such as lymphoma, leukemia, etc.), active Immunosuppressive treatment (Chemo, Steroids, etc.) (Immunocompromised, defined in [ANNEX 2](#). **IMMUNOCOMPROMISED ICD-10 CODE LIST**).

WHO guidelines on COVID-19 therapeutics include the following groups

- **High risk:** people who are immunosuppressed; estimated hospitalization rate of 6%.
- **Moderate risk:** >65 years of age, conditions like obesity, diabetes and/or chronic conditions including chronic obstructive pulmonary disease, kidney or liver disease, cancer, with disabilities, and with comorbidities of chronic disease; estimated hospitalization rate of 3%.

- **Low risk:** those who are not in the high or moderate risk categories; low risk of hospitalization (0.5%) – most people are low risk.

Data will be evaluated looking at frequency and percentage of COVID-19 patients who will fall in those criteria to understand strongly recommended or conditionally recommended use of Paxlovid™ in comparison to the country of issue recommendations.

### **9.8. Quality Control**

Quality control for each project is performed by a specific audit team member assigned to the study. Quality control practices include, but are not limited, to:

- Having qualified individuals who did not have a role in the study review data analyses and any final study report documentation for accuracy
- Ensuring proper documentation of data sources and key analytical steps
- Auditing all software programs and results both with respect to computer output and final tables
- Performing internal consistency checks of data presentations
- Aligning dissemination materials with external requirements.

Regarding statistical programming, each program undergoes interim tests to ensure the program is working as expected. A study member will apply one or more testing methods as appropriate.

### **9.9. Limitations of the Research Methods**

This is a retrospective observational study and therefore can only demonstrate association and not causality. The results of this study may not be generalizable to the entire population.

### **9.10. Other Aspects**

Not applicable.

## **10. PROTECTION OF HUMAN PARTICIPANTS**

### **10.1. Patient Information**

The EHR database is unstructured data. Individual medical records will be extracted, anonymized and entered into the eCRF.

All parties will comply with all applicable laws, including laws regarding the implementation of organizational and technical measures to ensure protection of participant personal data. Such measures will include omitting participant names or other directly identifiable data in any reports, publications, or other disclosures, except where required by applicable laws.

Participant personal data will be stored at the study site in encrypted electronic form and will be password protected to ensure that only authorized study staff have access. RCSI Bahrain will implement appropriate technical and organizational measures to ensure that the personal data can be recovered in the event of disaster. In the event of a potential personal data breach, RCSI Bahrain shall be responsible for determining whether a personal data breach has in fact occurred and, if so, providing breach notifications as required by law.

To protect the rights and freedoms of natural persons with regard to the processing of personal data, when study data are compiled for transfer to Pfizer and other authorized parties, any participant names will be removed and will be replaced by a single, specific, numerical code, based on a numbering system defined by Pfizer. All other identifiable data transferred to Pfizer or other authorized parties will be identified by this single, participant-specific code. The investigator site will maintain a confidential list of patients who participated in the study, linking each participant's numerical code to his or her actual identity. In case of data transfer, Pfizer will maintain high standards of confidentiality and protection of patients' personal data consistent with the clinical study agreement and applicable privacy laws.

### **10.2. Participant Consent**

As this study does not involve data subject to privacy laws according to applicable legal requirements, obtaining informed consent from patients by Pfizer is not required.

### **10.3. Institutional Review Board (IRB)/Ethics Committee (EC)**

There must be prospective approval of the study protocol, protocol amendments, and other relevant documents (eg, informed consent forms if applicable) from the relevant IRBs/ECs. All correspondence with the IRB/EC must be retained. Copies of IRB/EC approvals must be forwarded to Pfizer.

### **10.4. Ethical Conduct of the Study**

The study will be conducted in accordance with legal and regulatory requirements, as well as with scientific purpose, value and rigor and follow generally accepted research practices described in Guidelines for Good Pharmacoepidemiology Practices (GPP) issued by the International Society for Pharmacoepidemiology (ISPE), Declaration of Helsinki and its amendments, and any applicable national guidelines. This study will follow the

Strengthening the Reporting of Observational Studies in Epidemiology (STROBE) reporting guideline.

## 11. MANAGEMENT AND REPORTING OF ADVERSE EVENTS/ADVERSE REACTIONS

This study protocol requires human review of participant-level unstructured data; unstructured data refer to verbatim medical data, including text-based descriptions and visual depictions of medical information, such as medical records, images of physician notes, neurological scans, x-rays, or narrative fields in a database. The reviewer is obligated to report adverse events (AEs) with explicit attribution to any Pfizer drug that appear in the reviewed information (defined per the participant population and study period specified in the protocol). Explicit attribution is not inferred by a temporal relationship between drug administration and an AE but must be based on a definite statement of causality by a healthcare provider linking drug administration to the AE.

The requirements for reporting safety events on the non-interventional study (NIS) adverse event monitoring (AEM) Report Form to Pfizer Safety are as follows:

- All serious and non-serious AEs with explicit attribution to **any Pfizer drug** that appear in the reviewed information must be recorded on the data collection tool (eg, chart abstraction form) and reported, within 24 hours of awareness, to Pfizer Safety using the NIS AEM Report Form.
- Scenarios involving drug exposure, including exposure during pregnancy, exposure during breast feeding, medication error, overdose, misuse, extravasation, lack of efficacy, and occupational exposure associated with the use of a Pfizer product must be reported, within 24 hours of awareness, to Pfizer Safety using the NIS AEM Report Form.
- For exposure during pregnancy in studies of pregnant women, data on the exposure to Paxlovid™ during pregnancy, are not reportable unless associated with serious or non-serious adverse events.
- For these AEs with an explicit attribution or scenarios involving exposure to a Pfizer product, the safety information identified in the unstructured data reviewed is captured in the Event Narrative section of the report form, and constitutes all clinical information known regarding these AEs. No follow-up on related AEs will be conducted.

All the demographic fields on the NIS AEM Report Form may not necessarily be completed, as the form designates, since not all elements will be available due to privacy concerns with the use of secondary data sources. While not all demographic fields will be completed, at the very least, at least one patient identifier (eg, gender, age as captured in the narrative field of the form) will be reported on the NIS AEM Report Form, thus allowing the report to be considered a valid one in accordance with pharmacovigilance legislation. All identifiers will be limited to generalities, such as the statement “A 35-year-old female...” or “An elderly male...” Other identifiers will have been removed. Additionally, the onset/start dates and stop

dates for “Illness,” “Study Drug,” and “Drug Name” may be documented in month/year (mmm/yyyy) format rather than identifying the actual date of occurrence within the month/year of occurrence in the day/month/year (DD/MMM/YYYY) format.

All research staff members must complete the following Pfizer training requirements:

- “Your Reporting Responsibilities (YRR) with Supplemental Topics.”

These trainings must be completed by research staff members prior to the start of data collection. All trainings include a “Confirmation of Training Statement” (for signature by the trainee) as a record of completion of the training, which must be kept in a retrievable format. Copies of all signed training statements must be provided to Pfizer.

## **12. PLANS FOR DISSEMINATING AND COMMUNICATING STUDY RESULTS**

A final study report detailing the final study protocol and the analysis results will be provided when the study is complete. In the event of any prohibition or restriction imposed (eg, clinical hold) by an applicable competent authority in any area of the world, or if RCSI Bahrain is aware of any new information which might influence the evaluation of the benefits and risks of a Pfizer product, Pfizer should be informed immediately.

## 15. LIST OF FIGURES

None.

## ANNEX 1. LIST OF STANDALONE DOCUMENTS

None.

## ANNEX 2. ADDITIONAL INFORMATION

**Table 6. Additional Variables**

Category	Variables of Interest
Comorbidities	

• Cancer (active or history of cancer)

• Chronic kidney disease (CKD) at any stage

• Chronic liver disease (cirrhosis, non-alcoholic fatty liver disease, alcoholic liver disease, autoimmune hepatitis)

• Chronic lung diseases

• Chronic lung diseases: Interstitial lung disease, pulmonary fibrosis

• Chronic lung diseases: COPD, emphysema and chronic bronchitis

• Chronic lung diseases: Asthma (moderate to severe)

• Chronic lung diseases: Cystic fibrosis

• Chronic lung diseases: Pulmonary embolism

• Chronic lung diseases: Pulmonary hypertension

• Chronic lung diseases: Bronchopulmonary dysplasia

• Chronic lung diseases: Bronchiectasis

• Dementia or other neurological conditions

• Diabetes (type 1 or type 2)

• Down syndrome

• Heart conditions (heart failure, coronary artery disease, or cardiomyopathies)

• HIV infection

• Hypertension

• "Immunocompromised state (primary caused by genetic defects; secondary/acquired from prolonged use of corticosteroids or other immune weakening medicines)"

• Immunocompromised state: HIV/AIDS

PFIZER CONFIDENTIAL

CT24-WI-GL02-RF02 4.0 Non-Interventional Study Protocol Template For Secondary Data Collection Study

15-Jun-2022

Page 31 of 41

Category	Variables of Interest
	

• Immunocompromised state: Solid malignancy

• Immunocompromised state: Bone marrow transplant

• Immunocompromised state: Organ transplant

• Immunocompromised state: Rheumatologic/inflammatory

• Immunocompromised state: Primary immunodeficiency

• Immunocompromised state: Other immune conditions

• Immunocompromised state: CKD or ESRD

• Immunocompromised state: Hematologic malignancy

• Immunocompromised state: IS drug only

• Immunocompromised state: Anti-metabolites

• Immunocompromised state: >1 IC condition

• Mental health conditions (mood disorders, including depression, and schizophrenia spectrum disorders)

• Overweight and obesity

• Pregnancy and recent pregnancy (for at least 42 days following end of pregnancy)

• Sickle cell disease (SCD) or thalassemia

• Smoking, current or former

• Solid organ or blood stem cell transplant (includes bone marrow transplants)

• Stroke or cerebrovascular disease

• Peripheral vascular disease

• Transient Ischemic Attack

• Substance use disorders (alcohol, opioid, or cocaine use disorder)

• Tuberculosis

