### 9.2.2. Exclusion Criteria

**There are no exclusion criteria for this study.**

## 9.3 Variables

The following variables are used to obtain comprehensive descriptive results.

1. Demographics
2. Date of symptoms
3. Viral variant analysis where available (type of viral variant ie, omicron, delta etc.)
4. PCR date along with CT Value

5. Co-morbidities and
6. BMI if  $\geq 30$
7. Symptoms at presentation
8. COVID 19 vaccine status (NB 92% of population has been vaccinated -with at least one dose of COVID 19 vaccine- in Bahrain)
9. Hospital admission
10. Follow up looking at compliance and reason of non-compliance
11. Day 5,7, 21 and 28 symptoms for COVID-19 patients who receive and HRU limited to admission (ICU, ward, need for oxygen therapy) or death
12. Date of symptoms resolution if applicable

**Table 2** Table 2 below depicts the patient demographics that will be accessed during the baseline and follow-up periods. The baseline period is defined as one year before the index date. Comorbidities (full list in [Table 6](#)) and maintenance medication usage for chronic conditions (eg, statins, antihypertensives, etc.) will be described during the baseline period and follow-up periods and are listed in [Table 3](#).

Risk factors for severe COVID-19, intensive care unit (ICU) usage, invasive mechanical ventilation (IMV) usage, supplemental oxygen use, non-invasive ventilation, and high-flow nasal cannula usage are depicted in [Table 5](#) and will be extracted from the *I-Seha* national electronic health record database.

Where applicable, emerging treatment patterns may be assessed as the time from symptom onset to COVID-19 diagnosis, time from symptom onset to treatment initiation, and the time from COVID-19 diagnosis to treatment initiation as illustrated in [Table 5](#).

10Nov23 WHO recommendations for Paxlovid treatments to define: 1. COVID-19 patients who meet the WHO criteria for “strongly recommended” 2. COVID-19 patients who meet the WHO criteria for “conditionally recommended”, and 3. COVID patients who are not falling into categories 1 or 2 will be used.

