**Table 3. Clinical Characteristic Variables**

Variable	Operational definition
Comorbidities	A full list of comorbidities is detailed below and according to eCRF: Distribution of patients diagnosed with each comorbid condition during the baseline and follow-up periods. Comorbid conditions will include, but are not limited to, asthma, emphysema, chronic obstructive pulmonary disease (COPD), hypertension, diabetes, obesity, cerebrovascular disease, neurological disease, chronic kidney disease, chronic liver disease, malignancy, etc.
Risk Factors for Severe COVID-19	Distribution of patients with each of the following risk factors during the baseline and follow-up periods: 

• Age <math>\geq 50</math> years

• Obesity (BMI <math>\geq 30</math>)

• Chronic kidney disease (eGFR <math>\geq 30</math> ml/min)

• Diabetes Mellitus

• Primary and Secondary Immunosuppressive disease or immunosuppressive treatment

• Cardiovascular disease (including congenital heart disease) or hypertension

• Chronic lung diseases (for example, chronic obstructive pulmonary disease, asthma [moderate-to-severe], interstitial lung disease, cystic fibrosis, and pulmonary hypertension)

• Sickle cell disease

• Neurodevelopmental disorders (for example, cerebral palsy) or other conditions that confer medical complexity (for example, genetic or metabolic syndromes and severe congenital anomalies)

• Having a medical-related technological dependence (for example, tracheostomy, gastrostomy, or positive pressure ventilation [not related to COVID-19])

Death	Distribution of patients who died on or after the enrollment date in the follow up period.

PFIZER CONFIDENTIAL

CT24-WI-GL02-RF02 4.0 Non-Interventional Study Protocol Template For Secondary Data Collection Study

15-Jun-2022

Page 17 of 41

Variable	Operational definition
Inpatient Death	Distribution of patients who died during a hospitalization in the follow-up period.

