1.0 Demographics			
1.1 Age	-		
1.2 Gender	-		
2.0 Clinical Characteristics	-		
2.1 Comorbidities (ICD-10)	-		
2.2 Vaccination Status (incl. date)	-		
2.3 Baseline Medication Usage	-		
2.4 COVID-19 Symptom (incl. date)	-		
2.5 COVID Diagnosis Date (index)	-		
Outcome Variables	-		
3.0 HRU	-		
3.1 Hospitalizations	-		
3.2 Outpatient Visits	-		
3.3 Emergency Room Visits	-		
3.4 Procedures	-		
3.5 Laboratory Tests (incl. COVID-Related)	-		
4.0 Medical Costs (incl. COVID-Related)	-		
4.1 Outpatient Costs	-		
4.2 Inpatient Costs	-		
4.3 Emergency Room Costs	-		
4.4 Ancillary Costs	-		
5.0 Pharmacy Costs (incl. COVID-Related)	-		

	Treated COVID-19 patients (N = n) Control Group Untreated COVID-19 patients (N = n)
6.0 Medication Usage (incl. written date of prescription and fill history)	-
6.1 Antibiotic	-
6.2 Antiviral (incl. Paxlovid™, COVID-19 monoclonal antibodies)	-
6.3 Antithrombotic	-
6.5 Anti-inflammatory (incl. steroids)	-

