## **ANALYSIS SETS/POPULATIONS**

### **1.5 FULL ANALYSIS SET**

The full analysis set will consist of approximately 8263 adult COVID-19 patients with pre-existing comorbidities who attended outpatient clinics in the Kingdom of Bahrain. It includes approximately 3000 patients who received Paxlovid and approximately 1000 COVID-19 patients who were offered Paxlovid therapy but who refused treatment.

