**Table 2: Clinical Characteristic Variables**

Variable	Operational definition
Comorbidities	Asthma, emphysema, chronic obstructive pulmonary disease (COPD), hypertension, diabetes, obesity, cerebrovascular disease, neurological disease, chronic kidney disease, chronic liver disease, malignancy, etc.
Risk Factors for Severe COVID-19	
 
• Age <math>\geq 50</math> years
 
• Obesity (BMI <math>\geq 35</math>)
 
• Chronic kidney disease (eGFR <math>\geq 30</math> ml/min)
 
• Diabetes Mellitus
 
• Primary and Secondary Immunosuppressive disease or immunosuppressive treatment
 
• Cardiovascular disease (including congenital heart disease) or hypertension
 
• Chronic lung diseases (for example, chronic obstructive pulmonary disease, asthma [moderate-to-severe], interstitial lung disease, cystic fibrosis, and pulmonary hypertension)
 
• Sickle cell disease
 
• Neurodevelopmental disorders (for example, cerebral palsy) or other conditions that confer medical complexity (for example, genetic or metabolic syndromes and severe congenital anomalies)
 
• Having a medical-related technological dependence (for example, tracheostomy, gastrostomy, or positive pressure ventilation [not related to COVID-19])
 

PFIZER CONFIDENTIAL

CT24-WI-GL03-RF03 2.0 *Non-Interventional Statistical Analysis Plan For Secondary Data Collection*  
 Study 01-Jun-2020  
 Page 9 of 22

Patient-reported COVID-19 symptoms	List of COVID-19 symptoms to be added by study team (US, CDC definition). 
 
1- Stuffy or runny nose
 
2- Sore throat
 
3- Shortness of Breath
 
4- Cough
 
5- Low energy/Tiredness/fatigue
 
6- Muscle ache/body aches
 
7- Headache
 
8- Chills or shivering
 
9- Feeling hot/feverish
 
10- Nausea or vomiting
 
11- Diarrhea
 
12- Loss of sense of smell
 
13- Loss of sense of taste
 

Death	Died on or after the enrollment date in the follow up period
Inpatient Death	Died during a hospitalization in the follow-up period

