## **HANDLING OF MISSING VALUES**

Missing data patterns, including the amount of missing data for each variable and individual and possible reasons for missing data, will be explored. As this is a descriptive study, missing data will not be imputed. The number and percentage of patients with missing data will be reported for each variable.

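### The BMI item is collected only at 30 or more, so it cannot supply the overweight category in protocol Table 6 or show whose BMI was never measured

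*Protocol*

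**What the plan says.** Protocol section 9.3 numbers the variables to be collected. Item 5 is comorbidities; item 6 is BMI, limited to values of 30 or more. The same section cites Table 6 in Annex 2 as the full list of comorbidities, which "will be described during the baseline period and follow-up periods and are listed in" Table 3. Table 6 includes "Overweight and obesity" with no cut-off.

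The obesity definition differs between the documents. Protocol Table 3 has "Obesity (BMI \geq 30", and protocol section 9.7 agrees. SAP Table 2 has "Obesity (BMI \geq 35", as do the SAP's study population and its table shell for clinical characteristics. No SAP table has an overweight row.

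The protocol's sample results table labels its comorbidity row "2.1 Comorbidities (ICD-10", and the SAP shell does likewise. Protocol Table 3 says comorbidities follow the eCRF, which is not among the documents.

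On missing data the SAP says: "As this is a descriptive study, missing data will not be imputed". It adds: "The number and percentage of patients with missing data will be reported for each variable". Age, sex and provider specialty have an unknown or missing category in both documents. BMI has none in either.

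**The concern.** A field filled only above a threshold loses two things. It cannot grade patients below the threshold, so overweight disappears from it. Its blanks also have two meanings, below 30 and never measured, so completeness cannot be counted.

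Describing comorbidities in treated and untreated patients is the primary objective. Obesity is also:

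- a risk-factor row with a p-value and effect size in the SAP shell;
- part of the comorbidity and high-risk characteristics listed for propensity-score matching;
- named in the WHO moderate-risk group used for secondary objective 1.

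On the last of these, the SAP lists age 50 or over as a ground for being offered treatment, whereas the WHO moderate-risk group starts above 65. A patient aged 50 to 65 offered treatment on age alone, whose obesity was never charted, could therefore be placed in the low-risk group.

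The source is routine, unstructured charts, and patients who qualified through age or diabetes did not need a BMI to do so. Some gaps in BMI are plausible, although neither document gives a completeness figure.

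**Working it through.** **What the field can and cannot show**

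| True state | Entry under item 6 as worded | What an analyst can tell |
|---|---|---|
| BMI 30 or more, measured | filled | obese |
| Overweight, below 30, measured | blank | nothing |
| Normal weight, measured | blank | nothing |
| BMI never measured | blank | nothing |

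Three different states share one entry. Neither the overweight category nor the missing count can be rebuilt from this field.

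**Illustration of size.** The documents give no obesity prevalence and no BMI completeness, so there is no plan figure to reproduce. The inputs are:

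- Group sizes, from SAP section 1.5: "It includes approximately 3000 patients who received Paxlovid and approximately 1000 COVID-19 patients who were offered Paxlovid therapy but who refused treatment".
- Alpha 0.05, from the SAP's inferential statistics; two-sided is assumed.
- True obesity of 20%, 30% or 40%, equal in both groups: assumed.
- Share with BMI unmeasured, 5% to 30%: assumed, and unrelated to BMI within each group.
- Blanks counted as not obese: assumed.

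Reported prevalence = true prevalence × (1 − share unmeasured).

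With 40% true obesity and 10% v 20% unmeasured:

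- Treated: 0.40 × 0.90 = 36%, or 1080 of 3000. Controls: 0.40 × 0.80 = 32%, or 320 of 1000.
- Pooled proportion = 1400/4000 = 0.35. SE = √[0.35 × 0.65 × (1/3000 + 1/1000)] = 0.0174.
- z = 0.04/0.0174 = 2.30, p = 0.02.
- Unpooled SE = √(0.36 × 0.64/3000 + 0.32 × 0.68/1000) = 0.0172, so the 95% CI is 4.0 ± 3.4, or 0.6 to 7.4 points.

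The chance of a significant result when there is no true difference is approximately Φ[(|d| − 1.96 × SE pooled)/SE unpooled]:

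| Unmeasured, treated v control | True 20% | True 30% | True 40% |
|---|---|---|---|
| 5% v 10% | 1.0 point, 10% | 1.5 points, 15% | 2 points, 20% |
| 10% v 20% | 2 points, 30% | 3 points, 46% | 4 points, 63% |
| 10% v 30% | 4 points, 84% | 6 points, 97% | 8 points, >99% |
| equal shares | 0 points, 5% | 0 points, 5% | 0 points, 5% |

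Equal missingness still lowers prevalence: 40% is reported as 32% when 20% are unmeasured in each group. If a true difference exists, say 40% v 35%, the ratio stays at 1.14 while the difference shrinks from 5.0 to 4.0 points at that level.

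**Treating every blank as missing instead.** In the 10% v 20% example, 3000 − 1080 = 1920 treated (64%) and 1000 − 320 = 680 controls (68%) would be reported as missing, against true shares of 10% and 20%. Everyone with an entry would be obese. Neither treatment of blanks gives both a usable prevalence and a correct missing count.

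**With the value and a not-recorded code.** The same example gives 1080/2700 = 40% and 320/800 = 40%, with 300 and 200 reported as not recorded.

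**The case against.** The strongest reply is that item 6 is a terse list entry and need not be the only source. Overweight is itself requested under item 5 through Table 6, comorbidities carry an ICD-10 label, and the unseen eCRF may hold more. Item 6 may also be a yes/no obesity item, which could have an unknown option. This stands against the reading that overweight patients cannot be identified at all: the documents do not support that, and the limit applies to the BMI field. It does not remove the mismatch. The only code list supplied is for immunocompromise, an absent code is as ambiguous as a blank, and a yes/no item at 30 would yield neither overweight nor the SAP's category at 35.

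A reader might also infer that the plan will bias obesity prevalence and the group comparison. That goes too far. No passage counts blanks as not obese, and doing so sits badly with the no-imputation rule. But that rule works only if the analyst can see which values are missing, which this field prevents.

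Nor do the documents show unequal recording. Both groups were outpatients offered treatment under the same criteria, BMI among them. The calculation also ignores the propensity-score matching the SAP mentions.

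Finally, it is true that no SAP output uses overweight, and that reading an absent record as absent disease is a general limit of chart review. Here, though, the loss comes from the collection rule, and measured values would be discarded.

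**Conclusion.** The mismatch stands on the text alone. Item 6 as worded cannot supply overweight below 30 and cannot separate a BMI below 30 from an unmeasured one, so the SAP's per-variable missing count cannot be met for BMI.

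The effect on results is conditional. Prevalence is understated only if blanks are taken as not obese, and a false group difference requires unequal recording as well. Under the assumptions shown, that difference runs from 1 to 8 points, and is zero with equal missingness. These figures show sensitivity; they do not predict what the study will report.

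The point merits a change before abstraction, because analysis cannot restore values that were never extracted. The conflict between 30 and 35 is a separate, documented inconsistency on the same variable.

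**What to change.** - Change protocol section 9.3, item 6, to record the BMI value, or height and weight, whenever available, with an explicit not-recorded code. Make the eCRF match.
- Define overweight and obesity as categories derived from that value, so that Table 6 and the analysis use one source. If ICD-10 diagnoses are also used, state how they combine with it.
- In the SAP shell, give by group the number with no BMI, and report obesity as a percentage of those with a recorded BMI.
- Reconcile the protocol's cut-off of 30 with the SAP's 35. A recorded value supports either.

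The percentage among those measured is unbiased only if recording does not depend on BMI. The not-recorded count lets readers bound the effect: in the example, 36% to 46% in treated patients and 32% to 52% in controls, taking all unmeasured patients as not obese and then as obese.

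The cost is one extra eCRF value per chart already under review and slightly more abstraction time. Leaving it until after abstraction would mean reopening charts, from a cohort of 8263 records.
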